5.1.1.5 Health Outcomes Data Analyses

The Supplemental Dry Eye Patient Reported Outcomes Questionnaire is a series of questions designed to gather information about the types and severity of dry eye symptoms that are experienced by patients in each eye. Health outcomes data will be summarized by treatment group for the mITT Population as shown in [Table 5-28](#).

Table 5-28 Health Outcomes Data Summaries

Endpoint	Description	Timing	Methodology
Treatment satisfaction	Summary of raw score by analysis visit	Cycle 1: Weeks 4, 8, 12, and 24	Continuous descriptives

Endpoint	Description	Timing	Methodology
		Cycle 2: Weeks 4R, 8R, and 12R	

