2.2 List of Figures

Figure 4-1	Stage 1 Study Flow – Dose Escalation In Patients With Moderate To Severe Dry Eye Disease.....	10
------------	---	----

3. List of Abbreviations and Definition of Terms

Table 3-1 Abbreviations and Definitions of Terms

Abbreviation/Term	Definition
AE	adverse event
BCVA	best-corrected visual acuity
CFB	change from baseline
DDE	Drug Dictionary Enhanced
█	█
eCRF	electronic case report form
F1	█
F2	█
IOP	intraocular pressure
MedDRA	Medical Dictionary for Regulatory Activities
mITT	modified intent-to-treat
OSDI	Ocular Surface Disease Index
PK	pharmacokinetic
PT	preferred term
SAE	serious adverse event
SAP	statistical analysis plan
SOC	system organ class
TEAE	treatment-emergent adverse event
TBUT	tear film break-up time
VAS	visual analog scale
WHO	World Health Organization

4. Introduction

This statistical analysis plan (SAP) details comprehensive, technical specifications of the statistical analyses of the safety, exploratory efficacy, and health outcomes data outlined and/or specified in Protocol 192371-024 Amendment 6, dated 19 Jan 2017. Study 192371-024 is a 2-stage, Phase 2 study. A final database lock will occur after the completion of stage 2. Separate analysis plans will be prepared for the analysis of each stage. This document is the analysis plan for stage 1. Specifications of tables, figures, and data listings are contained in a separate document. The SAP for pharmacokinetic (PK) data will be prepared separately.

This document is organized into 3 main sections as follows:

1. Study overview
2. Statistical methodology and study endpoints
3. Data handling and analysis conventions

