5.1.1.1.3 Statistical Methodology

The methodologies defined in Table 5-2 apply as specified to individual endpoints defined in this SAP for stage 1.

Table 5-2 Statistical Methodology – Stage 1

Methodology	Description
Categorical counts	
 • Number of patients in individual categories 
 ○ Patients with ≥ 1 qualifying event counted once per individual category
Categorical descriptives	
 • Number and percentage of patients in individual categories 
 ○ Patients with ≥ 1 qualifying event counted once per individual category • N1 if percentage denominator \neq number of patients in the population (standard percentage denominator) 
 ○ N1 = patients with nonmissing value
Continuous descriptives	
 • N1, mean, SD, median, minimum, maximum • N1 = patients with nonmissing value
CFB descriptives	
 • Continuous descriptives for baseline, postbaseline, and CFB values • N1 = patients with nonmissing values at both baseline and the specified postbaseline analysis visit
Responder	
 • Categorical descriptives for responders and nonresponders • N1 = patients with nonmissing values at both baseline and the specified postbaseline analysis visit

CFB = change from baseline

Two treatment cycles are defined in this analysis plan. Treatment Cycle 1 includes all visits from study baseline (also called cycle 1 baseline) to Week 24 or Exit visit if a patient receives ██████████ throughout the study, or to the last visit before retreatment if a patient receives ██████████ during the study. For visits in treatment Cycle 1, refer to study windows in Section 6.2. Treatment Cycle 2 applies to patients who receive retreatment, and includes all visits from retreatment and thereafter. Visits in treatment Cycle 2 will be determined based on the study days relative to the retreatment visit using the study windows specified in Section 6.2.

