The study baseline value of an assessment will be the measurement prior to the treatment at Day 1 unless it is missing. In that case, the last nonmissing value recorded prior to the treatment (Day 1) will be used instead. The cycle baseline (also called cycle 2 baseline) value of an assessment will be the measurement prior to the retreatment at Week 12 from the first treatment unless it is missing. In that case, the last nonmissing value recorded prior to the retreatment (Week 12) will be used instead.

Ocular evaluation will be summarized by study eye and contralateral eye separately.

Some raw and derived data listings will be provided, and will be fully defined in the table, figure, and data listing specification document.

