6.6 Health Outcomes Endpoint Conventions

The supplemental dry eye questionnaire will be collected as shown in [Table 6-26](#).

Table 6-26 Supplemental Dry Eye Questionnaire

Dry Eye Symptoms Questionnaire	Score
In the last 7 days, have you experienced the following symptoms in your right (or left) eye? 
 1. Dryness 2. Sensitivity to light 3. Pain 4. Decreased or blurred vision 5. Tearing 6. Experienced feeling like something doesn't belong in your eye 7. Secretion or discharge 8. Burning or stinging 9. Redness 10. Swelling in the upper eyelid 11. Swelling in the lower eyelid 12. Irritation 13. Grittiness or feeling as if small specks of sand are in your eye 14. Discomfort 	Frequency: 
 • 0=All of the time • 1=Most of the time • 2=Half of the time • 3=Some of the time • 4=None of the time Severity: 
 • 0=Very mild • 1=Mild • 2=Moderate • 3=Severe • 4=Very severe
Treatment Satisfaction Questionnaire	

Dry Eye Symptoms Questionnaire	Score
Taking your entire treatment experience into consideration, if given the choice again, how likely would you be to repeat the procedure you received in your right (or left) eye?	
• 0=Very unlikely• 1=Unlikely• 2=Neither likely or unlikely• 3=Likely• 4=Very likely Mild

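### Does the Stage 1 SAP need summary tables for the 14 per-eye symptom items that Table 5-28 leaves out?

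*SAP*

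**What the plan says.** SAP 5.1.1.5 describes the questionnaire as "a series of questions designed to gather information about the types and severity of dry eye symptoms that are experienced by patients in each eye" and says health outcomes data are summarised for the mITT population as laid out in Table 5-28. That table has one endpoint, treatment satisfaction, specified as "Summary of raw score by analysis visit" with continuous descriptives at Weeks 4, 8, 12 and 24 and at Weeks 4R, 8R and 12R.

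SAP Table 6-26 gives the content of the instrument. For 14 symptoms it asks "have you experienced the following symptoms in your right (or left) eye" over the past week, with a frequency and a severity score for each. A separate satisfaction item asks "how likely would you be to repeat the procedure you received in your right (or left) eye". Protocol 6.3.1 presents the questionnaire as the Stage 1 health outcomes measure, built to assess the two eyes individually, and names the treatment satisfaction instrument for Stage 2.

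Three general rules bear on the point:

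- SAP 5.1.1.1.3: "Ocular evaluation will be summarized by study eye and contralateral eye separately".
- SAP 4: "Specifications of tables, figures, and data listings are contained in a separate document".
- SAP 6.2, in the conventions after the visit-window tables: all assessments go into their listings.

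**The concern.** In cohorts 2 to 6D one eye receives F1 or F2 and the other receives vehicle, so a symptom measure is most informative when it can be attributed to an eye. OSDI gives one score per patient and cannot be. The global evaluation in SAP 5.1.1.3.7 is per eye but is the investigator's rating. The 14 items are therefore the only patient-reported symptoms that the visible documents clearly show at eye level, and the SAP's list of tables has no summary for them. The item that is summarised concerns willingness to repeat the procedure, which is not a symptom.

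The codes raise a second doubt. Frequency starts at "0=All of the time" and ends at 4 for none of the time, while severity rises from 0 for very mild to 4 for very severe. A change of +1 is an improvement on the first scale and a worsening on the second. Severity has no code for an absent symptom. If the form left it blank in that case, the change-from-baseline rule, "N1 = patients with nonmissing values at both baseline and the specified postbaseline analysis visit", would drop patients whose symptom had resolved.

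At stake would be exploratory information on tolerability and symptoms, in a stage whose analyses are meant to inform later trials.

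**Working it through.** **Coverage.** Per eye, 14 symptoms × 2 scores = 28. For both eyes, 28 × 2 = 56 scores per patient per visit. Table 5-28 has 1 row and none of these scores. The VAS (Table 5-13) and OSDI (Table 5-14) are other instruments. The omission from the visible summary tables is real.

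**Effect on planned results.** No Stage 1 summary takes these items as input. SAP 5.1.2 sets the sample size empirically, and Table 5-2 contains only counts, percentages and descriptive statistics. Each planned table stays correct whether or not the items are tabulated.

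**What full tabulation would give.** Assume the Table 5-28 visits, the nine cohorts listed in SAP 5.1.1.1.2, full enrolment at the anticipated cohort sizes, and retreatment of every patient in 6C and 6D.

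| Cohorts | Patients | Visits | Cohort-visits | Patient-visits |
|---|---|---|---|---|
| 1, 2, 3, 4, 5A, 6A, 6B | 3 + 4 + 8 + 8 + 8 + 8 + 8 = 47 | 4 | 7 × 4 = 28 | 47 × 4 = 188 |
| 6C, 6D | 4 + 4 = 8 | 3 + 3 = 6 | 2 × 6 = 12 | 8 × 6 = 48 |
| Total | 55 | | 40 | 236 |

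- Table entries: 40 × 56 = 2,240.
- Each continuous-descriptives entry in Table 5-2 holds six statistics (N1, mean, SD, median, minimum, maximum): 2,240 × 6 = 13,440 numbers.
- Raw scores: 236 × 56 = 13,216.
- Ratio: 13,440 / 13,216 = 1.02.

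Allowing Week 24 for 6C and 6D patients who are not retreated (+2 cohort-visits) and cohort 5B (+4) gives 46 × 56 = 2,576 entries. Change-from-baseline descriptives report baseline, postbaseline and change, so they could triple the count.

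The summary would thus hold slightly more numbers than the data it summarises. In cohorts of 3 to 8 patients, a listing that shows both eyes of each patient carries the same information and keeps the pairing, which separate study-eye and contralateral-eye tables do not.

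**Consistency with the rest of the SAP.** Macroscopic and photographic hyperaemia are graded in four quadrants as well as globally, but Tables 5-22 and 5-25 tabulate only the global assessment. Tabulating part of what is collected is this SAP's practice elsewhere.

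**Scoring.** Opposite code directions matter only if the scores are tabulated or combined, and the visible SAP plans neither. An absent symptom is already recorded by frequency code 4. Whether severity is left blank depends on the form's skip pattern, which is not in the available text. The codes are therefore not shown to be deficient.

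**The case for a change.** The best case for a change is textual. SAP 4 presents the document as a comprehensive technical specification that includes health outcomes. Where a listing alone is meant, the SAP says so, as it does for cup/disc ratio in 5.1.1.4.5.4. Section 5.2.2 records a change to the mITT definition but no decision to leave the symptoms untabulated. The listing convention sits among the visit-window rules, and 5.1.1.1.3 promises only some listings. On this reading the instrument's main content has simply been overlooked, and one sentence would settle it.

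The description stands: a reader of 5.1.1.5 cannot tell whether the items are to be listed only or tabulated elsewhere. The need for a change does not follow. The data are collected whatever Table 5-28 says, and SAP 4 leaves the detail of tables and listings to a separate document that may already cover them. A listing-only sentence would put a policy on paper without altering any analysis. Tabulating a subset is a matter of preference on which statisticians could reasonably differ.

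The argument that eye-level symptoms are otherwise lost is also uncertain. The VAS item table (Table 6-18) is redacted. If the VAS was asked per eye, the rule in 5.1.1.1.3 would already give a symptom summary by eye, though for nine symptoms rated on the day and not 14 over a week. If it was asked per patient, the eye-level tables that remain (Schirmer, TBUT, staining) show signs and not symptoms, and the objection keeps its force on that point.

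**Conclusion.** The observation is correct: Table 5-28 summarises none of the 28 symptom scores per eye. It does not call for a change to the plan. No test, estimate or stated conclusion in Stage 1 depends on these items. In cohorts of 3 to 8 patients a full tabulation would return about 1.02 numbers for every raw score. This is a gap in description that the table and listing specification, or a sensible analyst, fills. Any symptom table made later would be descriptive and should be labelled as not prespecified.

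The conclusion assumes that the listing convention in SAP 6.2 extends to the questionnaire items; the counts also assume the Table 5-28 visits and the anticipated cohort sizes. The separate specification, the visit schedule for this instrument, the VAS items and Protocol 7.3.2 are not visible, so no departure from a protocol commitment can be claimed or ruled out.

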5.1.1.6 Subgroup Analyses

Subgroup analyses are not planned for stage 1.

5.1.1.7 Interim Analyses

An interim database lock of stage 1 will not be conducted until after all patients in Cohorts 1 through 6B complete the study and all patients in Cohorts 6C and 6D complete at least Week 1 following retreatment. Statistical analyses will be performed following the database lock to support the design of future clinical studies.

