11.4	Glossary of Abbreviations.....	106
11.5	Protocol Amendment 1 Summary	108
11.6	Protocol Amendment 2 Summary	111
11.7	Protocol Amendment 3 Summary	113
11.8	Protocol Amendment 4 Summary	115
11.9	Protocol Amendment 5 Summary	118

11.10 Protocol Amendment 6 Summary	126
--	-----

List of Tables

Table 1	Dosage/Dose Regimen – Stage 1 Dose Escalation in Patients With Moderate to Severe Dry Eye Disease.....	12
Table 2	Dosage/Dose Regimen – Stage 2: Baseline Dose and Retreatment in Patients With Moderate to Severe Dry Eye Disease	13
Table 3	SCHEDULE OF VISITS AND PROCEDURES: Stage 1.....	20
Table 4	SCHEDULE OF VISITS AND PROCEDURES: Stage 2.....	22
Table 5	Investigator Procedure Assignments.....	24
Table 6	Stage 2: Randomization/Stratification Groups	41
Table 7	Baseline Treatment and Retreatment Regions	44

List of Figures

Figure 1	Stage 1 Study Flow – Dose Escalation in Patients With Moderate to Severe Dry Eye Disease.....	14
Figure 2	Stage 2 Study Flow – Baseline Dose and Retreatment in Patients With Moderate to Severe Dry Eye Disease	15

Structure:

Stage 1: multicenter, randomized, investigator-masked, dose escalation, vehicle-controlled

- single-dose, paired-eye comparison
- paired-eye comparison, retreatment at week 12 (cohorts 6C and 6D)

Stage 2: multicenter, randomized, investigator-masked, parallel treatment groups, vehicle-controlled

- single dose, bilateral treatment at baseline
- bilateral retreatment at week 12

Duration:

Stage 1: The duration per patient will be approximately 26 weeks (from screening to week 24 visit).

Stage 2: The duration per patient will be approximately 26 weeks (from screening to week 24 visit).

Study Treatment Groups:

Stage 1: Vehicle, F1 [redacted] and F2 [redacted]

Baseline and retreatment cohort 6C and 6D: F1 [redacted] and F2 [redacted]

Stage 2: Baseline and retreatment groups: up to 3 dose groups: vehicle, CFI [redacted], and CFI [redacted]

Controls:

Stage 1: sham [redacted] treatment, vehicle

Stage 2: vehicle

Dosage/Dose Regimen:

Stage 1 will sequentially examine the safety of doses [redacted] of F1 and F2 administered [redacted]

[redacted]

[redacted]

[redacted]

[redacted]

[redacted]

[redacted]

[redacted]

[redacted]

[redacted]

[redacted]

[redacted]

[figure not shown]
[redacted]

[redacted]

[redacted]y,

Approval Date: 19-Jan-2017

[Redacted text block]

Approval Date: 19-Jan-2017

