2.2 Clinical Hypotheses

[REDACTED]

[REDACTED]

[REDACTED]

significant safety findings [REDACTED], the remaining 2 patients in cohort 2 will be given a [REDACTED] vehicle in one eye and [REDACTED] F1 [REDACTED] in the other eye. After 2 weeks of monitoring, and in the absence of significant safety findings [REDACTED], four patients in cohort 3 will receive [REDACTED] vehicle in one eye and [REDACTED] F1 [REDACTED] in the other eye. After 2 weeks of monitoring the fourth patient in cohort 3, [REDACTED]

[REDACTED]
[REDACTED]
[REDACTED]
[REDACTED]
[REDACTED]

Four patients in cohort 4 will receive [REDACTED] of vehicle in one eye and [REDACTED] F1 [REDACTED] in the other eye. Two weeks after dosing the fourth patient in cohort 4, [REDACTED]

[REDACTED]
[REDACTED]

In the absence of significant safety findings from the first 4 patients in cohort 4, cohorts 5A and 6A will begin. For cohort 5A, patients will be administered [REDACTED] F1 [REDACTED] in one eye and [REDACTED] vehicle in the other eye. After 2 weeks of monitoring the first 4 patients in cohort 5A, [REDACTED]

[REDACTED] If there are no significant safety findings for the first 4 patients in cohort 5A, the dosing of the remaining 4 patients in cohort 5A will proceed, and then the first 4 patients of cohort 5B will be administered [REDACTED] of F1 [REDACTED] in one eye and [REDACTED] vehicle in the other eye.

For cohorts 6A and 6B, patients will receive [REDACTED] either F2 or vehicle (see Figure 1 and Table 1). For cohorts 6C and 6D, patients will receive [REDACTED] of either F1 or F2 and vehicle (see Figure 1 and Table 1). The doses [REDACTED] associated with cohorts 6A, 6B, 6C, and 6D will be determined [REDACTED] The progression from cohort 6A to 6B will be conducted in the same manner as for cohorts 3 through 5, with decisions to continue with dosing of a given cohort and/or to escalate to the next higher dose cohort based upon [REDACTED]

[REDACTED]
[REDACTED]
[REDACTED]

Approval Date: 19-Jan-2017

[Redacted text block]

[Redacted text block]

[Redacted text block]

[Redacted text block]

[Redacted text block]

[Redacted text block]

[Redacted text block]

[Redacted text block]

Approval Date: 19-Jan-2017

[REDACTED]

4 Study Population and Entry Criteria

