5.10 Retreatment

In stage 1 of the study, patients in cohorts 6C and 6D will be retreated (at week 12) [REDACTED]

[REDACTED]

[REDACTED]

[REDACTED]

[REDACTED]

To help guide the investigator's decision on retreatment, [REDACTED] unless a $\geq +2$ hyperemia grade [REDACTED] is present, at which time the investigator may elect not to retreat the patient in stage 1. In this case, the

Approval Date: 19-Jan-2017

patient will not be retreated in either eye but continue to be observed for safety (see Table 3) for the duration of the study. [REDACTED]

For stage 2, patients in treatment groups 2 and 3 will be retreated (at week 12) with CFI in both eyes at the same dose used for the baseline (day 1) [REDACTED] Treatment group 1 patients will be retreated at week 12 with vehicle. If retreatment is not administered, the patient will continue to be observed for safety (see Table 4) and exited at the Week 24/Week 12R/Exit visit.

In stage 2, the investigator can elect to [REDACTED] if a $\geq +2$ hyperemia grade [REDACTED] is present. [REDACTED]

[REDACTED]

[REDACTED]

6 Response Measures and Summary of Data Collection Methods

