7.6 Interim Analyses

An interim database lock of stage 1 will not be conducted until after all patients in cohorts 1 through 6B complete the study and all patients in cohorts 6C and 6D complete at least week 1 following retreatment. An interim database lock of stage 2 will not be conducted until after all patients in stage 2 completed at least week 1 following retreatment. Statistical analyses will be performed following each database lock to support the design of future clinical studies.

8 Study Visit Schedule and Procedures

[Redacted]

Approval Date: 19-Jan-2017

[Redacted text block]

[Redacted text block]

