5.1.1.4.2 Adverse Events

Adverse events (AEs) are defined as shown in [Table 5-17](#).

Table 5-17 AE Terms

Term	Description
TEAE	An adverse event recorded on the eCRF would be considered treatment-emergent if either of the following conditions are met: AE onset date \geq first study treatment date; or AE onset date $<$ first study treatment date and either: 
 • the severity of the event worsened on or after the first study treatment date, or • the event became serious on or after the first study treatment date
SeriousTEAE	An event identified as TEAE that further meets SAE criteria at any time would be a serious TEAE.

SAE = serious adverse event; TEAE = treatment-emergent adverse event

AEs, encompassing abnormalities and surgeries reported as occurring after the Screening Visit, will be coded using MedDRA version 19.0 or newer. Unique patients reporting AEs in the following AE categories will be summarized by treatment group for the safety population as shown in [Table 5-18](#).

Table 5-18 AE Summaries

Parameter	Description	Timing	Methodology
Overall summary	Overall summary for the following categories: 
 • TEAEs (ocular vs. non-ocular) • Study drug-related TEAEs (ocular vs. non-ocular) • Study procedure-related TEAEs (ocular vs. non-ocular) • Serious TEAEs (ocular vs. non-ocular) • TEAEs leading to study 	From treatment start date until Week 24/Week 12R or early termination date, whichever comes first	Categorical descriptives

Parameter	Description	Timing	Methodology
	
discontinuation (ocular vs. non-ocular)
 
 Deaths 		
TEAEs ^a	
Overall summary and by SOC in alphabetical order, PT and worst severity
 
The worst severity is defined as the greater of the onset severity and maximum severity following onset recorded on the eCRF. If the same TEAE term has been reported more than once for a subject with different severity grades, the worst severity grade will be used in the tabulation.
	
From treatment start date until Week 24/Week 12R or early termination date, whichever comes first
	Categorical descriptives

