^a Study days are calculated based on the visit date – Treatment (Day 1) visit date + 1.

Table 6-6 Analysis Visit Definitions 5

Analysis Phase	Analysis Visit (Derived)	Target Number of Days from Treatment	Window ^a
Pretreatment	Study Baseline	Day 1	Treatment Day 1
Treatment	Week 4	Day 28	Treatment Day [2, 55]
	Week 12	Day 84	Treatment Day [56, 125]
	Week 24	Day 168	Treatment Day >=126

For endpoints with scheduled visits of Study Baseline (Day 1), Week 4, Week 12, and Week 24.

^a Study days are calculated based on the visit date – Treatment (Day 1) visit date + 1.

Table 6-7 Analysis Visit Definitions 6

Analysis Phase	Analysis Visit (Derived)	Target Number of Days from Treatment	Window ^a
Treatment	Week 8	Day 56	Treatment Day [2, 69]
	Week 12	Day 84	Treatment Day [70, 125]
	Week 24	Day 168	Treatment Day \geq 126

For endpoints with scheduled visits of Week 8, Week 12, and Week 24.

^a Study days are calculated based on the visit date – Treatment (Day 1) visit date + 1.

Table 6-8 Analysis Visit Definitions 7

Analysis Phase	Analysis Visit (Derived)	Target Number of Days from Treatment	Window ^a
Pretreatment	Study Baseline	Day 1	Treatment Day 1
Treatment	Week 12	Day 84	Treatment Day [2, 125]
	Week 24	Day 168	Treatment Day \geq 126

For endpoints with scheduled visits of Study Baseline (Day 1), Week 12, and Week 24.

^a Study days are calculated based on the visit date – Treatment (Day 1) visit date + 1.

Table 6-9 Analysis Visit Definitions 8

Analysis Phase	Analysis Visit (Derived)	Target Number of Days from Treatment	Window ^a
Pretreatment	Study Baseline	Day 1	Treatment Day 1
Treatment	Week 24	Day 168	Treatment Day \geq 2

For endpoints with scheduled visits of Study Baseline (Day 1), and Week 24.

^a Study days are calculated based on the visit date – Treatment (Day 1) visit date + 1.

6.2.2 Treatment Cycle 2

Table 6-10 Analysis Visit Definitions 1 (Retreatment)

Analysis Phase	Analysis Visit (Derived)	Target Number of Days from Retreatment	Window ^a
Pre-retreatment	Cycle Baseline	Day 1	Retreatment Day 1 (Week 12 from treatment start)
Retreatment	Day 1R	Day 2	Treatment Day [2, 4]
	Week 1R	Day 7	Treatment Day [5, 17]
	Week 4R	Day 28	Treatment Day [18, 41]
	Week 8R	Day 56	Treatment Day [42, 69]
	Week 12R	Day 84	Treatment Day \geq 70

For endpoints with scheduled visits of Cycle Baseline (Day 1), Day 1R, Week 1R, Week 4R, Week 8R, and Week 12R.

^a Study days from retreatment are calculated based on the visit date – retreatment visit date + 1.

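### At the Stage 1 interim lock, Table 5-18 would set crude TEAE percentages from 24 weeks of follow-up beside those of retreated cohorts 6C and 6D, followed for as little as about 13 weeks

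*SAP*

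**What the plan says.** SAP 5.1.1.7 sets two conditions for the Stage 1 interim lock. It comes "after all patients in Cohorts 1 through 6B complete the study", and it also requires that "all patients in Cohorts 6C and 6D complete at least Week 1 following retreatment". Protocol sections 7 and 7.6 say the same. Protocol 5.10 puts retreatment of 6C and 6D at Week 12, and the protocol synopsis runs each patient to Week 24. On the use of the results, protocol 7.6 says: "Statistical analyses will be performed following each database lock to support the design of future clinical studies".

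For adverse events, SAP Table 5-18 counts patients over one period: "From treatment start date until Week 24/Week 12R or early termination date, whichever comes first". The statistic is the number and percentage of patients (Table 5-2), shown by treatment group/cohort (SAP 5.1.1.1.2). Table 5-23, on slit-lamp increases of one or more grades, uses the same period. SAP 5.1.1.1.3 defines Cycle 1, which ends at the last visit before retreatment, and Cycle 2, which follows it. The by-visit endpoints use these cycles; Tables 5-18 and 5-23 do not. Exposure (Table 5-16) is counted from first administration to study exit.

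**The concern.** At this lock the single-treatment cohorts have complete follow-up, while the retreated ones may be little more than halfway. A crude percentage of patients with an event depends on how long they were watched, and the SAP gives no interim cut-off, common window or exposure-adjusted rate. For a 6C/6D patient still in follow-up, none of the end points named in the Table 5-18 window has been reached, and the exposure formula has no exit date to use. The undivided window also mixes events before and after retreatment, so the table cannot show which events followed the second administration.

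At stake is the reading of retreatment safety in an analysis meant to inform later designs. The 6C/6D percentages carry that question, and they are the ones cut short.

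**Working it through.** **Plan's own figure.** The cohort sizes in SAP 5.1.2 give 3 (cohort 1) + 3 × 4 (2, 6C, 6D) + 6 × 8 (3, 4, 5A, 5B, 6A, 6B) = 63, which matches the stated maximum. The retreated cohorts contribute at most 4 + 4 = 8 patients.

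**Follow-up at the lock.** SAP 6.2 sets the Week 12 target at Day 84, the Week 1R target at retreatment Day 7, and the Week 24 target at Day 168. Week 1R on target therefore falls on study Day 84 + 7 − 1 = 90, or 12.9 weeks, against 24 weeks. In round weeks, (12 + 1)/24 = 54%. This is a minimum. The lock also waits for cohorts 1 to 6B, so actual follow-up may be longer.

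**Direction relative to equal follow-up.** The share of patients with at least one event cannot fall as follow-up lengthens. Stopping 6C/6D early therefore lowers their percentage or leaves it unchanged. Cutting the other cohorts at 13 weeks would lower theirs or leave them unchanged. Either way, the gap moves in favour of 6C/6D or not at all.

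**Size with no acute effect of administration.** The documents give no adverse event rates, so a range is assumed. With a constant rate and 24-week risk P, the Week 13 percentage is 1 − (1 − P)^(13/24). For example, 1 − 0.70^(13/24) = 0.176 and 1 − 0.50^(13/24) = 0.313.

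**Adding an acute risk.** Let each administration carry an assumed acute risk a, on top of the background P.
- Single-treatment cohort at 24 weeks: 1 − (1 − a)(1 − P).
- Retreated cohort at 13 weeks: 1 − (1 − a)²(1 − P)^(13/24).
- The two are equal when a = 1 − (1 − P)^(11/24). Above that value the retreated cohort looks worse even at Week 13.

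| Assumed 24-week background risk P | Shown at Week 13 if a = 0 | Shortfall (points) | Acute risk at which the ordering reverses |
|---|---|---|---|
| 20% | 11.4% | 8.6 | 9.7% |
| 30% | 17.6% | 12.4 | 15.1% |
| 50% | 31.3% | 18.7 | 27.2% |
| 80% | 58.2% | 21.8 | 52.2% |

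**Two contrasting cases.**
- P = 50%, a = 10%: at a common 24 weeks the retreated cohort is higher, 1 − 0.9² × 0.5 = 59.5% against 1 − 0.9 × 0.5 = 55.0%. At the interim it shows 44.4% against 55.0%, so the true ordering is hidden.
- P = 30%, a = 30%: the interim shows 59.6% against 51.0%, so the retreated cohort already looks worse. It would reach 65.7% at 24 weeks.

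**Small numbers.** With P = 50% and a = 0, the chance that none of 4 patients has an event is 0.5^4 = 6% at 24 weeks and (1 − 0.313)^4 = 22% at Week 13.

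**The case against.** The strongest objection concerns direction. By Week 1R, 6C/6D have been treated twice, and Table 5-18 has its own procedure-related categories, so events may well cluster around administration. A reader might infer that 6C/6D must look safer than the single-treatment cohorts. The documents do not support that, and the reversal points above show why. What remains is the shift relative to equal follow-up, which cannot go against 6C/6D.

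Scheduled contact is also similar. Cohorts 1 to 6B have 7 post-treatment visits to Week 24 (Day 2 and Weeks 1, 2, 4, 8, 12, 24). Cohorts 6C/6D have 7 by Week 1R (Day 2, Weeks 1, 4, 8, 12, Day 1R, Week 1R). This has some force for Table 5-23, since a grade is recorded only at an examination. It has less for TEAEs, because patients are asked about the time since the last visit (protocol 8.12.1), so the interval from Week 12 to Week 24 still counts.

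By-visit summaries are split by cycle, the eyes within a patient have identical follow-up, and all adverse events are listed. This stands and narrows the point to Tables 5-18 and 5-23. With 4 patients per retreated cohort, percentages move in 25-point steps and no between-cohort test is planned. That also stands, but chance variation does not remove a systematic shift. The separate table specification might set an interim cut-off; it is not available, and the SAP text sets none.

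Three further inferences fail:
- The Week 1R lock condition may seem to contradict the escalation rule ("After 2 weeks of monitoring the first 4 patients in cohort 5A"). One governs a database lock and the other dose-escalation monitoring, so they do not conflict.
- Nothing visible says the interim settles retreatment safety.
- Efficacy cells from Week 4R onward that are still empty at the lock are incomplete, not biased.

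**Conclusion.** The point holds for the Stage 1 interim only. As written, the plan puts TEAE percentages from 24 weeks beside percentages from a minimum of about 13 weeks, and it does not separate pre- and post-retreatment events in 6C/6D. Under a constant event rate with no acute effect, the understatement is about 9 to 22 points for assumed 24-week risks of 20% to 80%. The size depends on those assumed rates and on actual follow-up at the lock. The observed ordering depends on the acute risk per administration and could go either way. By the final lock, 6C/6D will have reached Week 12R and the planned follow-up is equal. By-visit summaries and study-eye against contralateral-eye comparisons are unaffected throughout.

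**What to change.** In SAP 5.1.1.7, for the interim lock only:

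1. Add a between-cohort TEAE summary, and the same for Table 5-23, over the common window from Day 1 to the Week 12 pre-retreatment visit. For 6C/6D use the SAP's existing Cycle 1 boundary, and apply the same Week 12 cut to the other cohorts.
2. Show 6C/6D events after retreatment in a separate Cycle 2 block, headed by the days of follow-up actually observed. Calculate exposure to the data cut-off date for patients still in follow-up.
3. Label the interim post-retreatment results as incomplete, with full data to Week 12R at the final lock.

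This costs a few lines of SAP text and one extra cut of existing tables, with no new data. The price is a more limited interim statement on retreatment: the common window compares cohorts after one administration each, and the Cycle 2 block has no concurrent single-treatment cohort beside it.
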